**BOX 1. ACOG's 5 A's Treatment as Usual**

1. **ASK** the patient about smoking status at the 1st prenatal visit and follow-up with her at subsequent visits.
2. **ADVISE** the patient who smokes to stop by providing advice to quit with information about the risks of continued smoking to the woman, fetus, and newborn.
3. **ASSESS** the patient's willingness to attempt to quit smoking at the time. Quitting advice, assessment, and motivational assistance should be offered at subsequent visits.
4. **ADVISE** the patient who smokes to stop by providing advice to quit with information about the risks of continued smoking to the woman, fetus, and newborn.
5. **ASSESS** the patient's willingness to attempt to quit smoking at the time. Quitting advice, assessment, and motivational assistance should be offered at subsequent visits.

**B-EPIC Intervention.** Women enrolled in the intervention group will receive TAU plus B-EPIC, which includes four core components: 1) Individualized tobacco treatment plus supplemental counseling, 2) Biomarker validation and feedback, 3) Change in maternal thought process and adoption of healthy behavior (e.g. exercise, based on PI framework), and 4) Pharmacotherapy as needed (see Table 3 for a summary of the study design). The initial assessment for this intervention takes 60 minutes, with follow-up sessions typically lasting 15-20 minutes. All sessions occur prior to or after pre-scheduled perinatal appointments. The intervention will be led by a certified tobacco treatment specialist (CTTS) (see Box 2 for CTTS core competencies).

[figure not shown]
**CTTS Training:** An existing nurse in the intervention site will undergo training to become a Certified Tobacco Treatment Specialist (CTTS) through completion of an accredited certification program. A CTTS is a professional who possesses the skills, knowledge and training to provide effective, evidence-based interventions for tobacco dependence across a range of intensities. CTTS's are trained in core competencies for the delivery of tobacco dependence treatment consistent with established evidence. For example, the CCTS will follow-up

contact with participants to strengthen brief MI interventions. Assessment, motivational counseling, treatment planning for both cessation and relapse, which are tailored to the unique needs of tobacco users, are core skills used in the delivery of CTTS services. Further, women are empowered to avoid secondhand smoke exposure often resulting in adoption of a smokefree home (PI framework). These services can be provided to individuals and groups, in person, via telephone or using other platforms, such as online. Two healthcare providers (primary and backup) will be trained from the intervention site. In case of staff turnover, an alternative healthcare provider may require CTTS training at a later date to ensure no interruption of CTTS services.

**Box 2. Certified Tobacco Treatment Specialists Core Competencies**

1. Tobacco dependence knowledge
2. Counseling and motivational interviewing skills
3. Assessment skills
4. Individualized treatment planning
5. Pharmacotherapy knowledge
6. Relapse prevention
7. Competence in working with diverse population subgroups
8. Referral resources for additional support

**Table 3. Summary of Study Design**

Timepoints	B-EPIC -Taking Action	Biomarkers	Survey	Incentives
Baseline 2nd trimester (18-24 weeks)	
 
• Individualized tobacco treatment (every month-minimum) plus supplemental counseling
 
• Biomarker validation and feedback
 
• Focus and adoption of health behavior and change in maternal thought process (e.g. exercise) based on PI framework
 
• Pharmacotherapy as needed.
 
	
 
• Urinary Cotinine
 
• iCup Drug & Quantitative Analysis
 
	
 
• Prenatal History
 
• Demographics
 
• Adverse Childhood Events (ACE)
 
• Outcomes Measures Survey (SOMs). Refer to Table 4
 
	\$20 gift card
3rd trimester (30-36 weeks)		
 
• Urinary Cotinine
 
• iCup Drug & Quantitative
 
	
 
• Prenatal History
 
• SOM
 
	\$20 gift card
Postpartum (1-2 months)		
 
• Urinary Cotinine
 
• iCup Drug & Quantitative
 
	
 
• Labor and Birth History
 
• Newborn History
 
• SOM
 
	\$40 gift card
Postpartum (5-6 months)		
 
• Urinary Cotinine
 
• iCup Drug & Quantitative
 
	
 
• Maternal and Infant Outcomes
 
• SOM
 
	\$40 gift card*

\*If 3 of 4 timepoints are completed, participants receive an additional \$20.

## Measures

**Biological Measures.** Urine cotinine assay. Smoking cessation will be defined by a urine cotinine assay  $<100$  ng/mL. Nonsmokers will be defined by urine cotinine  $\leq 99$  ng/mL, and conventional smokers will be defined by urine cotinine  $\geq 100$  ng/mL.

**Urine Screen for Drugs-of-Abuse.** The iCup Drug Screen (BioScan Screening Systems, Inc., Smyrna, TN) will be used to validate illicit drug use. The iCup employs enzyme-linked immune assays (ELIZA) to detect the presence or absence of the following drugs/drug classes: buprenorphine, morphine/opiates, methadone, oxycodone, benzodiazepines, amphetamines, methamphetamine, cocaine, and THC.

**Survey Measures.** Refer to Table 4 for validation studies key outcome measures.

**Tobacco Measures: cigarette, e-cig and dual use.** All participants will be cigarette smokers. The measurement of cigarette use (i.e., self-report of number of cigarettes smoked per day, e-cig usage, etc.,) is relatively straightforward; the measurement of e-cig use has previously presented challenges.

**Measures of cigarette and e-cig dependence.** Foulds et al., (2014) developed a valid measure of e-cig dependence (PSEDI), as well as a very similar measure for cigarette smokers. Thus, we plan to use this measure of dependence in conjunction with the established Fagerstrom Test of Nicotine Dependence.

**Measures of non-tobacco substance use.** Pregnant women in this study are all opioid dependent receiving buprenorphine. Their urine will be tested at the four assessment time-points for non-tobacco substance use.

**Measures of SHS exposure and psychosocial symptoms.** SHS exposure is a known barrier to persistent perinatal smoking and relapse. We will use the Edinburgh Postnatal Depression Scale (EDPS), the gold standard for measuring depressive symptoms during and after pregnancy. Maternal anxiety and perceived stress will be measured using the validated tools, (GAD, PSS respectively) to determine number of adverse childhood events (abuse and neglect) and intimate partner violence, the Adverse Childhood Events (ACE) and Hurt, Insult, Threaten and Scream (HITS) validated tools will also be used.

**Measures of birth and infant outcomes** are summarized in Table 4 and will be collected from the maternal and infant medical records and national MEPS data up to 6 months after delivery.

**Covariates.** Covariates will include demographic variables (age in years, education level, marital status, race/ethnicity), tobacco use and cessation history (e.g., average number of cigarettes smoked per day, severity of nicotine dependence, readiness to quit smoking), SHS exposure (smokers in the home), psychosocial measures (depression, anxiety, stress), use of other prescription medications (number), substance use severity (as measured by composite scores in the ASI-Lite), number of recent days of illicit substance use (using ASI for alcohol and other illicit drug use specifically illicit opioids, cocaine, marijuana/THC, benzodiazepines, and methamphetamine), and urine drug test results (positive/negative for marijuana, non-prescribed opioids, benzodiazepines, cocaine, methamphetamine). Covariates will be measured at baseline and at each data collection time-point (with the exception of demographic variables, which are not expected to change) Given the pilot nature of this study and the number of control variables, ability to detect differences in groups may not be possible; however, these data will provide critical information about what baseline demographic, psychosocial and substance use characteristics may be most associated with outcomes.

**Aim 3 Measures:** Using methods described by Drummond and Gold we will assess the reasonableness of the B-EPIC intervention's costs in relation to clinical outcomes achieved and examine the potential for program costs to be offset by reductions in health care utilization. Three types of economic measures will be collected during

intervention and follow-up periods. First, measures of direct intervention costs will be constructed from logs and records detailing staff time, equipment, facilities, and supplies used in the routine, ongoing operation of the intervention. These costs will be tracked on a continuous basis throughout the intervention period. Steps will be taken to discern costs associated with the research from those actually generated by the intervention, and to distinguish program start-up costs from ongoing maintenance costs. Second, measures of medical indirect costs and lifestyle indirect costs will be constructed using participant-reported measures of health care utilization and tobacco product utilization during each follow-up period along with measures of utilization from the medical record. Third, estimates of productivity-loss costs will be constructed using participant-reported measures of time lost from work, school, or usual activities due to illness, medical care, infant caregiving, and participation in intervention activities or other tobacco cessation programs (including the state tobacco quitline). Costs associated with medical care utilization will not be measured directly but rather will be estimated using national MEPS data on medical care costs associated with the utilization measures assessed in this study (e.g., hospital readmission, emergency department use).

These economic measures will allow for assessments of intervention cost-effectiveness from several different perspectives, including health care system, and society at large. Cost measures will be examined in relationship to improvements in proximal health outcomes to determine the within-trial, incremental costs and cost-effectiveness of the intervention relative to usual care. Within-trial measures of the cost per unit change in health outcome (e.g. preterm, low birth weight) will be constructed for this purpose.

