**Table 2. Estimated retention at each perinatal period**

	2 nd Trimester (18-24 weeks)	3 rd Trimester (30-36 weeks)	Postpartum (1-2 months)	Postpartum (5-6 months)
Usual Care	50	45	39	28
B-EPIC	50	45	39	28
Total	100	90	78	56

**Inclusion criteria:** 1) current diagnosis of opioid dependence with participation in the buprenorphine treatment program; 2) less than 32 weeks gestation; 3) age 18-49 years old; 4) diagnosis of current tobacco use disorder; and 5) read or write in English. **Exclusion criteria:** Women are excluded if they have current prisoner status, current severe mental illness (e.g., bipolar disorder with current mania, current suicidal ideation), or alcohol or sedative/hypnotic dependence that requires medical intervention.

**Recruitment, Screening and Informed Consent:** Institutional Review Board (IRB) approval will be obtained from the University of Kentucky for this study. The screening, recruitment and retention plan is anchored by our previous work among pregnant and postpartum women who smoke. All study personnel will have completed human subjects training - and good clinical practice (GCP) research training. There will be two methods of recruitment: 1) study flyers will be posted in highly visible areas in the UKHC MAT clinics for pregnant/postpartum women and 2) the research nurse will provide an overview of the B-EPIC study in the buprenorphine treatment clinic for pregnant women. At conclusion of the overview, all women will be given a flyer in which they can either check that they are interested in screening for the study, verbally let the research nurse know they are interested in screening, and also be given the study recruitment phone number. Volunteers interested in the study will be screened for eligibility by research staff and those meeting initial eligibility screening criteria will be invited to come in for an in-person screening whereby informed consent will be completed before any study procedures are initiated (see Human Subjects).

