**Study Procedures.** Participants will be asked to provide urine samples and complete a survey at four times throughout the study (2nd and 3rd trimester, and 1-2 months, 5-6 months after delivery). There will be minimum of 8 weeks between individual data collection time periods. First, a survey available via iPad (paper/pen by request) will be administered by the research staff. The survey will take approximately 20 minutes to complete and will assess current and past use of tobacco products, demographic and psychosocial variables, stage of change, and personal characteristics; skip patterns will be used if indicated to minimize respondent burden. See Table 4. The survey will be stored on RedCap, a secure web-based data management system managed through the UK Clinical and Translational Research Center. The research nurse will then collect prenatal biomarkers (urine for cotinine and drug testing). [name] (PI) will train all study personnel collecting prenatal biomarkers consistent with procedures refined in previous studies. Participants will be informed their urine will be tested for cotinine (metabolite of nicotine) and other illicit drugs to confirm tobacco and/or illicit substance use at each data collection point and informed of their results in compliance with American Congress of Obstetricians and Gynecologists (ACOG) clinical standards. Participants will be informed their survey and biomarkers results will remain confidential. Confidentiality will be maintained through the use of non-identifying subject numbers; all study data will be saved daily on a secure server in a password-protected folder.

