Anxiety	Generalized Anxiety Disorder 7 (GAD-7) is a 7-item, self-reported survey for screening and severity measuring of generalized anxiety
Perceived Stress Scale (PSS)	A 4-item scale validated to assess prenatal stress
Adverse Childhood Events (ACE)	A 10-item self-report measure developed for the ACE study to identify childhood experiences of abuse and neglect.
Hurt, Insult, Threaten and Scream (HITS)	A 4-item scale providers use to assess risk for Intimate Partner Violence (IPV)
Birth and Infant Outcomes (medical record and Kentucky Medicaid Claims Data)	
Gestational Age at Birth: Preterm Birth	Age in weeks on delivery day, and based on first trimester or earliest ultrasound (ACOG). Preterm birth defined as gestational age < 37 weeks.
Birth Weight: Low Birth Weight	First infant weight on day of delivery (grams). Low birth weight defined as < 2500 grams on day of delivery.
Neonatal Abstinence Syndrome	19-item scoring system for NAS, modified Finnegan Scale.
Well-child and Sick Visits, Hospital Admission-Readmission, Length of Stay	The International Statistical Classification of Diseases and Related Health Problems (usually abbreviated as ICD) is a diagnostic code such as 388.30 for tinnitus, unspecified.
Biological Abstinent Measures	
Urine Cotinine	Cotinine <100 ng/mL will confirm abstinence for active tobacco use
Urine Screen for Drugs of Abuse	Negative urine screen for illicit substances (iCup). If positive for anything other than buprenorphine, then quantitative laboratory analysis.

\*Age, Race/Ethnicity/Income/Education/Partner Status will also be measured

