### Statistical Analysis Plan

One hundred pregnant women undergoing medically-assisted treatment (MAT) with buprenorphine for opioid dependence will be recruited and randomized to B-EPIC ( $n=50$ ) or TAU ( $n=50$ ).

**Data Analysis (to determine the impact of the B-EPIC intervention on smoking indicators as well as birth and infant outcomes; Aims 1-2).** Data analyses will be done using SAS 9.4, with an alpha level of .05; analyses for these two aims will be done by [name]. Descriptive analysis, including means and standard deviations or frequency distributions, will be used to summarize all study variables. Baseline comparisons of covariates between the intervention group and the control, and between those who complete the study and those who drop out will be done using t-sample t-tests, Mann-Whitney U tests, or chi-square tests of association. Primary outcomes to be compared between treatment groups will include tobacco indicators, such as smoking and illicit drug use status (abstinence via urine cotinine, iCup results), smoking frequency and readiness to quit (cigarettes per day and stages of change), and maternal-child measures (gestational age of birth, birthweight, NAS, NAS severity, early childhood respiratory and ear infections). The collected variables will include not only these primary outcomes and covariates, but also feasibility indicators, such as average number of sessions completed and ratings of intervention by participants randomized to the intervention group. We will also make group comparisons between other variables that may affect maternal-child outcomes, including SHS exposure, infant feeding status at discharge (breastfeeding vs. formula), and number of people in the home. Those factors with group differences (including demographic factors measured at baseline) will be used as covariates in the corresponding analysis of group comparisons of maternal-child outcomes over time. The primary analysis strategy for the first

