two study aims will be two-factor (group x time) repeated measures mixed models; these will be estimated using the MIXED procedure or group comparisons of continuous outcomes over time, including cigarette use and tobacco dependence. Generalized estimating equation (GEE), analyses with an exchangeable correlation structure will be used to assess for significant differences between groups and across time for categorical and dichotomous outcomes (e.g., preterm birth, NAS) using the SAS GENMOD procedure. The main effects of group and time and the interaction between them will be included in each model, and covariates will be added to control for group differences. As appropriate, post-hoc pairwise comparisons will be done using Fisher's least significant difference procedure for mixed models and using contrast statements for GEE models.

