effect (i.e., 0.20), the power of the repeated measures mixed model will be at least 60% to detect a group effect and 87% to detect a time or interaction effect. While an algorithm for estimating the power associated with a generic GEE model has not been developed, this strategy is analogous to a repeated measures application of logistic modeling. With at least 60 mother/baby dyads completing the study and an alpha level of .05, the power of logistic regression to detect an odds ratio of 2.5 or larger will be at least 68%. While this level of power is not optimal, inclusion of 4 time-points in the GEE models will increase the power of this analysis technique relative to a logistic model for a fixed point in time; this phenomenon is consistent with the comparison of the expected power of a two-sample t-test relative to expected power of a repeated measures comparison of two groups over 4 time-points, namely power for the later exceeds the former under the same conditions. Given the paucity of research regarding tobacco cessation in this at-risk population, it is unknown whether a medium (or slightly smaller) effect size is appropriate for continuous outcomes, such as cigarettes per day. However, in a preliminary study of this population by our group (EMPOWR, described above), we found that 14% of pregnant women decreased their cigarette consumption between intake (typically during the second trimester) and the third trimester. This is notable since each participant chose a health goal to work on (including reducing stress, reducing alcohol/drug use, reducing smoking, or weight management), so not all would have focused on decreasing cigarette consumption. While smoking cessation is the ultimate goal of this intervention, prior research has demonstrated that cutting cigarette consumption below 8 cigarettes per day is a risk reduction strategy for preventing low birthweight, so we will consider outcomes of both successful cessation as well as reduction in consumption for this exploratory project. In addition, a prior study (using a different cessation intervention but with a similar sample size) has demonstrated that while pregnant women addicted to opioids were not able to quit smoking at a higher rate than those not exposed to the intervention, there was a significant increase in readiness to quit, as assessed via stage of change, in the intervention group relative to the controls. We are assessing changes in stage of change over time between the groups for this reason. For all of the inferential tests used in this study, the primary emphasis of these group comparisons will be to estimate effect sizes for the impact of the intervention, which will allow us to estimate power for future (larger) studies. We expect to be able to demonstrate group differences with this exploratory study, given the relatively modest effect sizes required to have a reasonable level of power to detect differences in outcomes between groups. As outlined above, the estimated effect sizes for the longitudinal analyses are expected to be conservative, given that they are based on the minimum expected sample size at the completion of the study; however, since the repeated measures modeling allows for the inclusion of participants who drop out prior to completion, the effective sizes for these group comparisons over time are actually underestimated.

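### The cotinine-abstinence GEE includes the baseline visit, when every woman is meant to be a smoker, and cessation is not tied to a baseline value

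*Combined protocol and SAP*

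**What the plan says.** - **Outcome.** The Statistical Analysis Plan lists among its primary outcomes "smoking and illicit drug use status (abstinence via urine cotinine, iCup results". Under Biological Measures, "Smoking cessation will be defined by a urine cotinine assay" below 100 ng/mL, and Table 4 repeats the cut-off: "Cotinine <100 ng/mL will confirm abstinence for active tobacco use". Neither place refers to the woman's own baseline value.
- **Visits.** "Participants will be asked to provide urine samples and complete a survey at four times throughout the study". Table 3 labels the first of these (second trimester) as baseline and takes urinary cotinine there.
- **Model.** Dichotomous outcomes go to a GEE with exchangeable correlation in SAS GENMOD. "The main effects of group and time and the interaction between them will be included in each model". Power Considerations adds that "inclusion of 4 time-points in the GEE models will increase the power".
- **Population.** Measures states "All participants will be cigarette smokers". The tobacco inclusion criterion is only "diagnosis of current tobacco use disorder", with no cotinine threshold and no explicit requirement of current cigarette smoking.
- **Not stated.** The plan gives no reference visit, no restriction to follow-up visits, no conditioning on baseline cotinine and no method for empty cells. Covariates enter only where the groups differ.

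**The concern.** Cotinine is sampled at four visits and four time-points are counted in the GEE, so the baseline visit is part of the response. At that visit the outcome is, by design, the same for everyone: nobody is abstinent. A logistic model with a separate parameter for each arm at each visit then has to estimate the log-odds of zero in two cells.

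The complementary case is a woman who is already below 100 ng/mL at entry. The plan's definition scores her as having ceased smoking, although nothing has changed. The last-observation-carried-forward rule for tobacco indicators could extend that status if she drops out.

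What is at stake is the quit comparison in Aim 1. The plan says its main emphasis is on estimating effect sizes for larger studies. If the reference visit and the contrast are left open, the analyst will choose them after seeing the model diverge.

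**Working it through.** **1. Empty baseline cells.** Inputs are 50 women per arm (Study Procedures) and no abstinence at baseline (Measures). The baseline log-odds are ln(0/50) in each arm, which is not finite. Any quantity that uses these cells inherits the problem.

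**2. What fails and what survives.** The follow-up counts are assumed, since the documents give none. TAU has 0, 4, 3, 3 of 50 abstinent at the four visits and B-EPIC has 0, 10, 9, 8 of 50, with no dropout and the same women abstinent across visits as far as the counts allow. Exchangeable logistic GEE fits:

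| Model | Result |
|---|---|
| Four visits, group x time, baseline as reference | intercept about -35, all standard errors undefined, convergence still reported; working correlation 0.60 |
| Four visits, group x time, last visit as reference | group log-OR at last visit 1.093 (SE 0.710, p = 0.12); follow-up interaction terms -0.037 (SE 0.361) and 0.142 (SE 0.141); baseline terms diverge |
| Three follow-up visits, group x time, last visit as reference | group log-OR 1.093 (SE 0.710), same interaction terms; working correlation 0.91 |
| Four visits, group + time only | group log-OR 1.122 (SE 0.650) |
| Three follow-up visits, group + time only | group log-OR 1.085 (SE 0.629) |

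Hand check of the last-visit contrast: ln[(8/42)/(3/47)] = 1.093. The divergent values depend on the software and stopping rule; the absence of a finite estimate does not. The correlation falls because the fitted baseline residuals are essentially zero.

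In 300 simulated trials with Table 2 retention (50/45/39/28 per arm) and assumed follow-up abstinence of 10% and 25%, the four-visit interaction model had a coefficient beyond +/-10 or an undefined standard error in all 300. The baseline terms alone trigger that criterion. With three visits the rate was 8%, from chance sparse cells.

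**3. If some women are negative at baseline.** Let k be the share in each arm who enter and stay below 100 ng/mL, and q the true quit rate among the rest. The observed rate is k + (1 - k)q. With q assumed to be 5% (TAU) and 15% (B-EPIC):

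| k | TAU | B-EPIC | OR | Share of TAU quits that are not quits, k / TAU rate |
|---|---|---|---|---|
| 0 | 5.0% | 15.0% | 3.35 | 0% |
| 2% | 6.9% | 16.7% | 2.71 | 29% |
| 5% | 9.75% | 19.25% | 2.21 | 51% |
| 10% | 14.5% | 23.5% | 1.81 | 69% |

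The probability of at least one empty baseline cell is 1 - [1 - (1 - k)^50]^2. This is 60%, 15% and 1% at k = 2%, 5% and 10%, so both problems can occur together when k is small.

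**4. The four-time-point argument.** That argument is offered in support of at least 68% power for an odds ratio of 2.5 with 60 completers. The 68% does not reproduce as a comparison of 30 with 30. The two-proportion normal approximation (two-sided 0.05) peaks near 38.5% against 61.0%, at Phi[(0.225 - 1.96 x 0.1291)/0.1258], about 41%. That is a separate matter and nothing here rests on it.

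The repeated-measures figures do reproduce. Take noncentrality N m f^2 / [1 + (m - 1)rho] with N = 60, m = 4 and rho = 0.3 (assumed; the plan states none). Then f = 0.25 gives 15/1.9 = 7.89 and 78.9% power (plan: 79%), and f = 0.20 gives 9.6/1.9 = 5.05 and 59.9% (plan: 60%). With three visits these become 11.25/1.6 = 7.03 and 74.1%, and 7.2/1.6 = 4.50 and 55.0%. This is a continuous-outcome analogue of counting one visit too many: about five percentage points.

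**The case against.** The strongest reply is that the follow-up comparison survives. A reader might infer that the planned model yields no usable group test at all, or that one empty cell in one arm breaks it. The documents do not support that. They name no reference visit and they provide for contrast statements after the GEE. With the last visit as reference, the four-visit fit returns the three-visit group contrast to three decimals. With one baseline-negative woman in TAU only (1, 5, 4, 4 of 50, B-EPIC unchanged), the last-visit log-OR is 0.784 (SE 0.648) with or without baseline. This part of the reply stands. It does not rescue the omnibus interaction test or a four-visit average from the interaction model.

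No sentence assigns cotinine to the GEE by name, and the examples given are preterm birth and NAS. But those occur once per pregnancy, whereas cotinine status is dichotomous, primary and measured four times. No competing reading is offered.

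The dilution figures rest wholly on assumed rates. Measures also calls women at or above 100 ng/mL conventional smokers, so the intent is that women are positive at entry. That stands: the gap is in the definition and the entry criterion, and its frequency is unknown.

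The time-point sentence covers GEE models in general, including drug-screen status, where baseline need not be degenerate. That also stands, so the correction concerns abstinence only.

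**Conclusion.** The concern holds in limited form and should be fixed. If Measures is right that all women smoke at entry, every term or test that uses the baseline visit in the planned interaction model lacks a finite estimate, and the working correlation is distorted. Follow-up group contrasts can still be obtained, so the defect lies in the specification and not in the data.

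The definition of cessation would also count an unchanged baseline-negative woman as a quitter. The fall in the odds ratio from 3.35 to between 2.71 and 1.81 is conditional on assumed quit rates of 5% and 15% and on 2% to 10% of women being negative at baseline; the documents support none of these rates.

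A reader might also infer that removing baseline-negative women is harmless because baseline is common to both arms. The documents do not establish this. Randomization follows consent and screening, no section places the baseline urine before it, and Table 3 puts the first sample and the intervention in the same baseline row.

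**What to change.** - **Data Analysis (Aims 1-2):** fit the abstinence GEE to the three follow-up visits only, with baseline cotinine as a covariate if wanted.
- **Biological Measures and Table 4:** define cessation as baseline cotinine at or above 100 ng/mL followed by a follow-up value below 100 ng/mL.
- **Randomization or Study Procedures:** state that baseline urine is taken before randomization, if that is so. Report the number of baseline-negative women by arm. Show the all-randomised result, in line with the intention-to-treat convention under Handling Missing Data, beside any analysis restricted to baseline-positive women.
- **Power Considerations:** say that abstinence has three informative time-points, not four.
- **Inclusion criteria and Measures:** reconcile the two on whether current cigarette smoking is required at entry.

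The cost is a few sentences. Baseline cotinine is already collected, so no new data are needed. A few women may leave the restricted denominator, and the power argument for this outcome has to cite three visits.
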